6.5 Contacts Between Study Visits

Telephone or e-mail contacts for safety evaluation will occur at the end of 9, 15, 21, 27, 33, 39, 45, 51, 57, 63, 69, 75, 81, 87, 93, 99, 105, 111 and 117 months of use (LNG20 36-45 year old enrollment group only through Month 93 and Mirena subjects only through Month 57). The contacts should occur within 14 days before or after the expected contact date.

- Review of adverse events or changes in medical history
- Review of concomitant medications
- Review contraception method history since last scheduled study contact. The IUS would be considered to be her primary method of contraception if no regular use of other contraception is indicated on the diaries.
- Complete Bleeding/Cramping Form
 - All subjects: Months 27, 33, 39, 45, 51 and 57
 - All LNG20 subjects: also Months 63, 69, 75, 81, 87, 93
 - LNG20 16-35 year old enrollment group: also Months 99, 105, 111 and 117
- Inquire about change in sexual partner. If a contact elicits that there has been a change in sexual partner since the last time the subject had STD testing, she should be asked to come to the office for an Unscheduled Visit for Chlamydia and gonorrhea testing. In addition, HIV and any other appropriate STD testing should be performed as per CDC recommendations.
- Interview subject regarding future plans for relocation or discontinuation
- LNG20 subjects who are beyond the Month 90 study visit at the time that an investigative site obtains Institutional Review Board approval of Protocol Version 9.0 will be informed about the amendment changes at the Month 93 telephone contact or, if the Month 93 telephone contact has already occurred, at an additional telephone contact.

- Telephone contact prior to any early IUS discontinuation:
 - Discuss contraception options in preparation for the upcoming Discontinuation Visit such that the subject can immediately initiate another method (the site should attempt to have her desired method available) or be abstinent to:
 - Avoid conception within 7 days after IUS discontinuation
 - Enable the subject to avoid undesired pregnancy
 - Request the subject not have intercourse for at least 24 hours before the Discontinuation Visit; the visit may need to be rescheduled if the subject has intercourse within 24 hours of IUS removal
- Confirmation of next scheduled appointment

6.6 Study Treatment Completion/Early Discontinuation

Study treatment completion will occur at the end of 60 months of Mirena IUS use, 96 months of LNG20 IUS use for the 36-45 year old enrollment group or 121 months of LNG20 IUS use in the 16-35 year old enrollment group. The visit should occur within 14 days before or after the completion of 60 months of Mirena use or 96 months for the LNG20 IUS 36-45 year old enrollment group; the visit should occur within 7 days before or after the completion of 121 months of use for the LNG20 IUS 16-35 year old enrollment group. The same assessments should be performed if Early Discontinuation occurs.

- Inquire about last intercourse; if possible, any subjects who had intercourse (with intravaginal ejaculation) within the preceding 24 hours should have the Discontinuation Visit rescheduled to a time more than 24 hours from intercourse.
- Collect diaries and review for appropriate completion. Confirm compliance with study IUS by reviewing contraception method(s) documented in diaries since the last scheduled study contact.
- Complete Bleeding/Cramping Form (**only if discontinuation after Month 24**)
 - Include only information since the last time the form was completed;
 - If the last study visit or contact (phone or email) was more than 3 months ago, only include the information for last 3 months;

- If Early Discontinuation is during Months 25- 27, include only information beginning with Month 25
- Review of adverse events or changes in medical history
- Review of concomitant medications
- Inquire about change in sexual partner
- Collection of blood sample for:
 - Hemoglobin if not done within the last 3 months
 - Plasma levonorgestrel (only if after Month 36 or for subjects participating in the PK Substudy) if not done within the last 3 months
- High sensitivity urine pregnancy test (if positive, see Sections 7.4 and 7.5)
- Weight and blood pressure
- Breast and pelvic exam (if not performed within the last 3 months)
- Any clinically indicated physical examination
- Pap test if indicated, see section 6.11
- STD testing:
 - Chlamydia testing for all subjects 25 years old or younger who have not had any testing within the last 6 months
 - Chlamydia and gonorrhea testing for any subject following a change in sexual partner since the last study visit. In addition HIV and any other appropriate STD testing should be performed as recommended by the CDC
- Removal of IUS, if not already expelled or removed (at an outside location)
- Retain all removed or expelled IUSs (when possible) per the Study Reference Manual
- Contraceptive counseling
 - Immediate initiation of another method in the office when possible
 - Request to use this method or be abstinent for at least one week to avoid conception within 7 days after IUS discontinuation
- Schedule next appointment

6.7 30-Day Safety Follow-Up

All subjects must have a safety follow-up visit between 30 and 43 days after the Treatment

Completion/Early Discontinuation Visit (except those made lost to follow up or who withdrew consent per section 7.18). If the subject contacts the office with an expulsion that was 30 or more days ago, this visit may be combined with the Early Discontinuation visit.

- Review of adverse events (note: all adverse events occurring within 30 days of IUS discontinuation should be reported on the appropriate adverse event CRF)
- Review of concomitant medications used up to 30 days of IUS discontinuation
- Menstrual history if not using a hormonal method of contraception
- High sensitivity urine pregnancy test (if positive, see Sections 7.4 and 7.5)
- Weight and blood pressure
- Additional contraceptive counseling if needed
- Review with subject that continued telephone or clinic follow-up (as appropriate) is indicated for the following:
 - an ongoing IUS-related adverse event at study discontinuation should be followed monthly until the adverse event resolves or has stabilized
 - any subject electing to use a non-hormonal contraceptive method or no contraception (including those desiring pregnancy) will be followed monthly for up to 3 months after IUS removal/expulsion for return of menses. Any woman who does not menstruate within 3 months following IUS discontinuation will be referred for appropriate evaluation and continue to be followed monthly until menses has occurred or a diagnosis for the cause of the secondary amenorrhea has been established
- Those women desiring a pregnancy after IUS discontinuation will be contacted every three months from their Treatment Completion/Early Discontinuation Visit up to one year to record return to fertility.
 - Once a pregnancy is reported no further follow-up contact is required.
 - Women who do not become pregnant and change their intention before completing a full 12 months of follow-up will be discontinued from the study and not be included in the return to fertility cohort.

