Subjects will receive detailed instructions on how to record vaginal bleeding, dysmenorrhea, and other contraceptive use in a daily diary during the first 24 months of study participation. Thereafter, only other contraceptive use will continue to be recorded daily on a diary for the remainder of study treatment in addition to the information collected at each study visit. After 24 months, bleeding and dysmenorrhea information only will be obtained for the remainder of study treatment via interviews by study staff during each study follow-up visit and contact (every 3 months) during treatment.

In addition, Levonorgestrel plasma levels will be obtained for all subjects at six month intervals and at IUS discontinuation visit beginning with Month 36 until Protocol Version 9 when thereafter, levonorgestrel plasma levels will be obtained in all subjects at IUS discontinuation and also annually in all women enrolled prior to 31May2011.

The Sponsor intends to retain all IUSs that are removed or expelled (when possible) and analyze an appropriate sample of these systems.

The following substudies will be performed at selected sites:

- Levonorgestrel PK data will be obtained in a subset of approximately 60 subjects (20 non-obese LNG20 subjects, 20 non-obese Mirena subjects and 20 obese LNG20 subjects). In

addition to all procedures outlined in Section 6 for the concomitant primary study visits, LNG plasma samples will be obtained at Enrollment (pre-IUS insertion), Weeks 1 and 2, and Months 1, 3, 6, 9, 12, 18, 24 and 30 after IUS insertion (includes three extra visits at Weeks 1 and 2, and Month 9, not included in the main study). These subjects will be required to give informed consent for participation in the levonorgestrel PK subset (See Section 4.4).

- A subset of 60 subjects assigned to LNG20 and completing 121 months of study treatment will have levonorgestrel samples obtained at various timepoints after IUS removal to characterize the LNG elimination profile. Each subject in this subset will be randomized to one timepoint (one extra visit) post-IUS removal (24 hours, 48 hours, 7 days or 14 days) such that fifteen subjects are randomized to each timepoint.
- A subset of 60 women assigned to LNG20 at selected sites will have transvaginal ultrasound evaluations at enrollment (pre-IUS insertion), 1 year, 5 years and 10 years (pre-IUS removal) to assess changes in endometrial thickness.

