4.4.3 Elimination PK Substudy

Subjects desiring to enter the elimination PK substudy must meet all of the following criteria:

- be 16-35 years old at the time of enrollment in the primary study
- have been assigned to LNG20
- have completed 121 months of LNG20 use
- have signed informed consent for the elimination PK sampling prior to randomization for the elimination PK sampling timepoint
- not use hormonal contraception and not attempt to become pregnant during substudy participation such that the subject agrees to one or more of the following criteria:
 - sexually abstinent for up to 2 weeks
 - use of a non-hormonal method of birth control for up to 2 weeks

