6.4 Post-Insertion Study Follow-Up Visits

Post-insertion study follow-up evaluations will occur at Months 1, 3, 6, 12, 18, 24, 30, 36, 42, 48, 54, 60, 66, 72, 78, 84, 90, 96, 102, 108, 114 and 120 (LNG20 36-45 year old group only through Month 90 and Mirena subjects only through Month 54). The visits should occur within 14 days before or after the expected calendar visit date (within 7 days for the Month 1 and 3 visits).

- Diaries
 - Collect diaries and review for appropriate completion.
 - Confirm menstrual bleeding and cramping information is entered correctly (Months 1, 3, 6, 12, 18, and 24 only)
 - Confirm other contraception use is entered correctly

- Confirm compliance with study IUS by reviewing other contraception method(s) documented in diaries.
- The IUS would be considered her primary method of contraception if no regular use of other contraception is indicated on the diaries
 - Dispense additional diaries as needed
- Medical review
 - Review of adverse events or changes in medical history
 - Review of concomitant medications
 - Complete Bleeding/Cramping Form
 - All subjects: Months 30, 36, 42, 48 and 54
 - All LNG20 subjects: also Months 60, 66, 72, 78, 84
 - LNG20 16-35 year old enrollment group: also Months 90, 96, 102, 108, 114 and 120
 - Inquire about change in sexual partner
- Collection of blood sample for
 - Hemoglobin
 - All subjects: Month 12
 - All LNG20 subjects: also Month 60
 - LNG20 16-35 year old enrollment group only: Also Month 120
 - Plasma levonorgestrel
 - All subjects: Months 36, 42, 48 and 54
 - LNG20 subjects enrolled prior to 31May2011:
 - LNG20 16-35 year old enrollment group: also Months 60, 72, 84, 96, 108 and 120
 - LNG20 36-45 year old enrollment group: also Months 60, 72 and 84
- Physical examination and testing
 - High sensitivity urine pregnancy test (if positive, see Sections 7.4 and 7.5)
 - Weight and blood pressure (both must be measured at each visit)
 - Breast exam
 - All subjects: Months 12, 24, 36 and 48
 - All LNG20 subjects: also Months 60, 72 and 84

- LNG20 16-35 year old enrollment group: also Months 96, 108 and 120
- Any clinically indicated physical examination
- Clinically verify presence of IUS by palpation or direct visualization of strings (for missing strings management see Section 6.14 and Appendix C)
- Pelvic exam
 - All subjects: Months 12, 24, 36 and 48
 - All LNG20 subjects: also Months 60, 72, 84
 - LNG20 16-35 year old enrollment group: also Months 96, 108 and 120

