Levonorgestrel plasma levels will be obtained for all subjects at 6 months intervals and at IUS discontinuation visit beginning with Month 36 until Protocol Version 9 when thereafter, levonorgestrel plasma levels will be obtained in all subjects at IUS discontinuation and also annually in all women enrolled prior to 31 May 2011. Descriptive statistics will be presented at each visit to summarize the plasma levonorgestrel levels over time.

- Levels following removal

Levonorgestrel plasma levels obtained at 24 and 48 hours and 7 and 14 days following removal after the entire duration of use will be summarized.

- Pharmacokinetic subset

Levonorgestrel plasma levels obtained in the PK subset will be summarized at each visit. Descriptive statistics will be presented for each visit and a graph will be presented of the mean levonorgestrel serum levels over time.

- IUSs that are removed or expelled during the study

Analysis of a sampling of retained IUSs will be summarized.

- **Endometrial Thickness**

Changes in endometrial thickness after one, five and 10 years will be compared to baseline.

- **Other Outcomes**

Changes in other outcomes such as, hemoglobin, physical exam, vital signs and pelvic exam including Pap test, will be summarized using descriptive statistics as appropriate.

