6. ANALYSIS POPULATIONS

The Safety population will include all subjects enrolled who underwent the IUS insertion procedure, regardless of age and outcome. Treatment assignment will be based on the treatment actually received.

The following subject populations will be used for efficacy analyses:

- Modified Intent-to-Treat (MITT) population will include all subjects between 16 and 35 years of age at study entry for whom the assigned IUS is successfully

placed in the uterus and for whom there is at least one assessment of pregnancy status after inserting the IUS.

- Per-Protocol (PP) population will include subjects in the MITT population with no major protocol deviations (to be identified prior to database cut-off).

The Treatment Pharmacokinetics (PK) population will include all subjects enrolled in the substudy and have at least one post-insertion PK assessment and no major protocol deviations.

The Elimination PK population will include all subjects enrolled in the substudy (who will be randomized to one time point post-IUS removal) and whose post-IUS removal PK assessment is not missing. The elimination PK sampling will only be obtained at the full intended duration of use IUS removal visit (i.e. Month 121).

The Endometrial Thickness (ET) population will include all subjects enrolled in the ET substudy and have at least one post-insertion ET measurement. The final endometrial thickness measurements will be obtained at baseline, Month 12, Month 60 and after the full intended duration of use (i.e. 10 years).

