10.3.3 Elimination PK

PK data will be summarized at each time point using descriptive statistics, including geometric means. Plasma concentrations over the first 14 days following LNG20 removal after 121 months of use will be summarized using the Elimination PK population. For the purpose of this analysis, all plasma concentrations below the limit of quantification occurring after the first measurable plasma concentration will be set to zero.

A population PK type analysis will be also performed.

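### The elimination PK summary names no pre-removal reference level, the draw that would supply it at Month 121 is waived for some women, and no rule covers a hormonal method started after removal

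*Protocol*

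**What the plan says.** Protocol 3.1 describes the substudy as "A subset of 60 subjects assigned to LNG20 and completing 121 months of study treatment", each woman randomised to one post-removal draw at 24 hours, 48 hours, 7 days or 14 days, with fifteen per time point. The stated aim is to characterise elimination.

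**Analysis.** Protocol 9.8 will summarise "Levonorgestrel plasma levels obtained at 24 and 48 hours and 7 and 14 days following removal". SAP 10.3.3 says: "Plasma concentrations over the first 14 days following LNG20 removal after 121 months of use will be summarized using the Elimination PK population". It specifies descriptive statistics per time point, including geometric means, and adds a population-type PK analysis without stating its data or model. Neither section mentions a pre-removal value.

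**Pre-removal sampling.** Under Protocol 6.4, women enrolled before 31 May 2011 have annual draws: "LNG20 16-35 year old enrollment group: also Months 60, 72, 84, 96, 108 and 120". At the completion visit, Protocol 6.6 lists "Plasma levonorgestrel (only if after Month 36 or for subjects participating in the PK Substudy) if not done within the last 3 months". The Synopsis, Protocol 2.2, 3.1 and 9.8, and SAP 3 say, with no such exemption, that every subject has a level taken when the IUS is discontinued.

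**Other hormones.** Protocol 4.4.3 requires that participants "not use hormonal contraception and not attempt to become pregnant during substudy participation". Protocol 6.6, written for all subjects, lists "Immediate initiation of another method in the office when possible". SAP 6 defines the Elimination PK population as women enrolled in the substudy "whose post-IUS removal PK assessment is not missing". The Treatment PK population in the same section excludes major protocol deviations; this one does not.

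**The concern.** An elimination profile describes a fall from a starting level. As written, the first point is at 24 hours and nothing anchors it. Each later point comes from different women, so differences between women add noise to the apparent decline. The plan does not link a woman's post-removal level to her own earlier level, although one should exist.

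The waiver also means that the available pre-removal level differs by enrolment date: Month 120 for some women, Month 121 for others. Finally, a woman who starts a levonorgestrel-containing method at removal would contribute drug from the new product to a table read as persistence of the old one. The SAP gives no instruction for that sample.

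**Working it through.** **Design figure.** 60 women / 4 time points = 15 per time point, as stated. No precision basis is given for 60.

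**Does the waiver reach every woman sampled at Month 120?**
- SAP 5.4: one month = 30.4 days. Protocol 6.4: Month 120 window ±14 days. Protocol 6.6: Month 121 window ±7 days.
- Shortest gap: 30.4 − 14 − 7 = 9.4 days. Longest: 30.4 + 14 + 7 = 51.4 days.
- Three months: 3 × 30.4 = 91.2 days. The gap is always shorter, so the waiver always applies.

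**How many substudy women are affected?** The documents do not say; it could be 0 to 60. If accrual were uniform from 1 November 2009 to 30 April 2013 (an assumption using the planned dates), 576/1,276 days = 45% enrolled before 31 May 2011, or about 27 of 60 if the substudy drew evenly on completers.

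**Is Month 120 a usable stand-in for Month 121?** Protocol 1.2 gives an initial release of about 20 mcg/day, and 7.1.1 projects 5.0 at ten years. A straight line falls (20 − 5.0)/120 = 0.125 mcg/day per month, or 2.5% of 5.0. Over 51.4/30.4 = 1.7 months that is about 4%. This assumes linear decline and plasma levels that track release.

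**Precision.** The documents give no CV or correlation, so both are assumed. The log-scale SD is s = √ln(1 + CV²), taken as equal before and after removal. At CV 50%, s = √ln 1.25 = 0.472. With n = 15, t(14) = 2.145 and t(28) = 2.048. The 95% CI factors (multiply or divide) are:
- Raw geometric mean at one time point: exp(2.145 × 0.472/√15) = 1.30.
- Ratio of two time points in different women: exp(2.048 × 0.472 × √(2/15)) = 1.42.
- Within-woman post/pre ratio: the SD is s√(2(1 − ρ)). At ρ = 0.5 it is 0.472, giving 1.30; at ρ = 0.7 it is 0.366, giving exp(2.145 × 0.366/√15) = 1.22; at ρ = 0.9, 1.12.

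Over CV 30% to 70%, the between-time-point factor runs from 1.25 to 1.60 and the within-woman factor at ρ = 0.7 from 1.13 to 1.31. Differences in half-life between women would widen both at later times. Comparing two time points on the percentage scale still uses different women: at ρ = 0.7, exp(2.048 × 0.366 × √(2/15)) = 1.31 instead of 1.42; at ρ = 0.5 there is no gain.

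**One woman of 15 on a levonorgestrel method** (illustrative), at r times the level of the others:
- Geometric mean multiplied by r^(1/15): 1.17 at r = 10, 1.22 at r = 20.
- Arithmetic mean multiplied by (14 + r)/15: 24/15 = 1.6 at r = 10, 34/15 = 2.3 at r = 20.

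**The case against.** The case against is substantial.

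- **A reader might infer that no starting level exists.** The documents do not support that. An adherent woman has a Month 121 level or, if that draw was waived, a Month 120 level. What is missing is its use in the analysis.
- **A reader might infer that between-woman differences bias the profile.** They do not: women are randomised to time points, so the groups are comparable on average. The cost is noise.
- **The raw summary is not the only analysis.** A population PK model is a standard way to handle one sample per woman at staggered times, and it could use earlier levels. This stands, but with data and model unstated it cannot be relied on to supply the reference.
- **A reader might infer that hormonal users are knowingly retained, or that 4.4.3 and 6.6 are irreconcilable.** Neither follows. Entry requires agreement to avoid hormonal methods, and a non-hormonal method started in the office satisfies both sections. The gap concerns women who break that agreement, and only a levonorgestrel-containing method would be measured directly as persistence. No frequency is given. The planned geometric mean moves far less than the arithmetic mean, and a median hardly at all.
- **Raw levels answer the stated outcome**, which is plasma levels after removal, and the analysis is descriptive. This stands, so percentages belong beside raw levels rather than in their place.

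**Conclusion.** The point holds as a gap in the written analysis. SAP 10.3.3 and Protocol 9.8 describe elimination without a named time zero, although the value should be in the database. The gain from using it depends on within-woman correlation: at an assumed CV of 50%, a decline is estimated to within a factor of about 1.22 at correlation 0.7 or 1.30 at 0.5, against 1.42 for two time points in different women. Even with no gain in precision, the profile would acquire the starting level it lacks.

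The 3-month waiver conflicts with the rule that all subjects are sampled at discontinuation, for an unknown number of substudy women. The consequence is modest if the Month 120 level serves as the reference. The population definition has no rule for post-removal hormonal use; the sizes shown for that are illustrations, not predictions.

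Priority is minor to moderate. This is a descriptive secondary objective, and nothing here touches the Pearl Index or the safety conclusions.

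**What to change.** **SAP 10.3.3.** Name each woman's last pre-removal level (Month 121 if drawn, otherwise Month 120) as time zero, and show it. Report her post-removal level as a percentage of it, alongside the raw levels. State that the population PK analysis uses these pre-removal values. Give medians as well as geometric means, because the section's zero rule for values below quantification would make any geometric mean that includes one equal to zero.

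**SAP 6.** Exclude from the Elimination PK population, and list, samples taken after a hormonal contraceptive was started following removal. Protocol 5.6 already records concomitant medication to 30 days after discontinuation, which covers the 14-day sampling period.

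**Protocol.** Reconcile the 3-month waiver in 6.6 with the all-subjects rule for substudy participants, and state that any Month 121 draw used as a reference precedes removal. Reconcile the in-office method start in 6.6 with the 4.4.3 agreement.

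**Cost.** The SAP changes are wording applied to data already collected, at the price of a few excluded samples. If the reconciliation drops the waiver, the addition is at most 60 tubes at a visit that already takes place.
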